4. PARTICIPANTS

We will conduct this vitamin D intervention study within MESA, an ethnically diverse, community-based cohort study. Up to three MESA cohorts will be approached for study recruitment. MESA originally recruited 6,814 participants in 2000-2002 from six U.S. communities: Forsyth County, NC; Northern Manhattan and the Bronx, NY; Baltimore City and [name]; St. Paul, MN; Chicago, IL; and Los Angeles County, CA. MESA Family participants are mainly siblings and parents of MESA Classic participants who were recruited in 2004-2006 for genetics-based studies. MESA Air New Recruit participants were recruited in 2006-2007 from three areas in Rockland County, NY; Riverside County, CA; and Coastal Los Angeles, CA. MESA oversampled by race/ethnicity to create a cohort that was approximately 40% White/Caucasian, 30% Black/African-American, 20% Spanish/Hispanic/Latino, and 10% Asian, primarily Chinese. All MESA Classic and Air New Recruit participants were free of clinical cardiovascular disease at the start of the study. Follow-up MESA examinations occurred 1.5, 3, 5, and 10 years after the baseline exam. A 15-year follow-up study visit (“MESA exam 6”) is ongoing and serves as the source population for this vitamin D trial.

We will recruit a total of 1,600 MESA study participants from five MESA field centers: Wake Forest University, Winston-Salem, NC; Columbia University, New York, NY; Northwestern University, Evanston, IL; University of California Los Angeles, Los Angeles, CA; and Johns Hopkins University, Baltimore, MD. MESA Classic Participants will be recruited at the time of their 6th MESA study examination, scheduled from September 2016 - March 2018. MESA Air and MESA Family participants will be recruited either during follow-up phone calls, or during a MESA INVITE-specific recruitment phone call. Inclusion criteria are active participation in MESA at one of the five field centers and willingness to participate in a clinical trial.

Exclusion criteria

1. Current use of >1,000 international units (IU) of cholecalciferol daily
2. Current use of any activated vitamin D product (calcitriol, paricalcitol, hectorol)
3. Known history of allergy or adverse reaction to vitamin D treatment
4. Known clinical history of primary hyperparathyroidism
5. Known clinical history of kidney stones within the previous 5 years
6. Current or previous history of maintenance kidney dialysis or kidney transplantation

7. Known clinical history of sarcoidosis

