8. Self-reported history of having elevated serum calcium levels
9. Serum calcium level >11 mg/dl at MESA Exam 1 (2000-2002)
10. Current participation in another interventional study
11. Inability to provide written informed consent

Standard over the counter vitamin D supplements and multivitamins typically contain between 400-800 IU of vitamin D₃ and *will be allowed* during this trial. If participants are taking >1000 IU of vitamin D daily but would like to participate in INVITe, they may participate if they reduce their total vitamin D supplement dose (from all vitamin D-containing supplements combined) to 1000 IU or less for at least 12 weeks prior to enrollment. Study staff will request that interested participants ask their health care provider whether it is safe for them to temporarily reduce their vitamin D supplement(s). Participants who temporarily reduce their vitamin D supplement(s) will wait at least 12 weeks from their last higher than 1000 IU vitamin D supplement dose prior to completing their baseline INVITe study visit. They can continue to take a total vitamin D supplement dose of up to 1000 IU daily (including 1000 IU daily) during both the 12-week temporary reduction and the 16-week study drug periods.

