6. TREATMENTS

6.1. Study drug and dosage. Participants randomized to active treatment will receive cholecalciferol (vitamin D₃) 2000 IU capsules daily (Carlson Labs, Arlington Heights, Illinois). Cholecalciferol is the most commonly used vitamin D supplement and can be purchased over the counter. The 2000 IU daily dosage meaningfully increases vitamin D stores, lowers circulating PTH concentrations, and can be safely added to pre-existing vitamin D supplements and usual dietary vitamin D intake while remaining safely below the tolerable upper intake (4000 IU daily) defined by the Institute of Medicine. Moreover, the 2000 IU dosage of cholecalciferol is currently used in ongoing vitamin D treatment trials, enhancing the applicability of this study.

6.2. Placebo. Participants randomized to placebo will receive identically appearing softgel capsules, which contain sunflower oil in gelatin/glycerin/water (Carlson Labs).

6.3. Duration. The 16-week treatment duration will reliably raise serum 25(OH)D concentrations, the accepted measure of vitamin D stores, to their steady state concentrations.

6.4. Adherence. Adherence will be assessed by participant return of unused treatment at the end of the 16-week study period.

6.5. Discontinuation. Participants will be withdrawn from the study drug if they experience a significant adverse reaction related to the study drug or an intolerable adverse reaction, such as a persistent allergy or rash, or if the patient withdraws consent. Premature termination of this clinical trial may also occur due to a regulatory authority decision, drug safety problems as determined by the Data Safety Monitoring Board (DSMB), or at the discretion of the funding agency (NHLBI).

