8. STUDY PROCEDURES

8.1. *MESA Exam 6.* For MESA Classic participants, baseline data and biosamples for this clinical trial will be obtained from existing procedures that are performed at MESA Exam 6. MESA-INVITe will use some of the MESA Exam 6 baseline data and biosamples, in accordance with the scientific aims and informed consent of the overall MESA study. Types of data that are collected as part of MESA exam 6 that may be used for MESA-INVITe include:

- Demographic information
- Medical and surgery histories
- Social habits (smoking and alcohol use)
- Prescription and non-prescription medication use
- Anthropomorphic measurements (height and weight)
- Blood pressure measurements
- Blood and urine collection

- DNA and RNA collection for epigenomic and transcriptomic analysis

Site investigators at each included MESA field center are co-investigators on this trial. The MESA exam 6 study visits are scheduled from September 2016 - March 2018. Study personnel will mail materials explaining the goals and procedures of this trial to MESA participants and will call participants prior to their Exam 6 visit to review eligibility. At the time of Exam 6, or soon after Exam 6, study personnel will approach potentially eligible subjects, confirm eligibility criteria, explain the details of the trial, and answer relevant questions. The MESA coordinating center will match all medications and supplements reported in the inventory to a known list of vitamin D containing medications in real time to determine the amount of current vitamin D use. For participants who are found to be suitable and interested in this study, MESA personnel will obtain informed consent, consult the MESA Coordinating Center for randomization, and distribute the study medication.

Participants who are unable to use their regularly scheduled Exam 6 as the baseline visit for MESA-INVITe (for example because study staff were unable to start MESA-INVITe at the scheduled Exam 6, or the participant elected to reduce their current vitamin D supplement use [Section 4]) may complete a separate “Exam 6-plus” to collect baseline MESA-INVITe measurements and dispense study medication. All MESA Family and Air participants will use Exam 6-plus visits for basement measurements. In these cases, “Exam 6-plus” will include informed consent, a medical history focused on MESA-INVITe eligibility criteria, vital signs measurement, phlebotomy, urine collection, and study drug dispensing.

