12. PROTECTION OF HUMAN SUBJECTS

12.1. Risks to the subjects

A. Human subjects involvement and characteristics

The purpose of this study is to determine individual level characteristics that modify the biological response to vitamin D₃ treatment. We will conduct a 16-week clinical trial of oral vitamin D₃ (cholecalciferol) therapy *versus* placebo among 1,600 participants from the MESA study, an ongoing NHLBI funded cohort study of cardiovascular disease. Participants will be recruited for this trial from five MESA field centers: Forsyth County, NC; Northern Manhattan and the Bronx, NY; Baltimore City and [name]; Los Angeles, CA; and Chicago, IL. MESA investigators from these field centers are co-investigators in this clinical trial. MESA originally recruited 6,814 adults who identified their race/ethnicity as White/Caucasian, Black/African-American, Chinese, or Spanish/Hispanic/Latino from six U.S. communities between July 2000 and August 2002. MESA excluded individuals who had any previous diagnosis of cardiovascular disease. All MESA participants gave informed consent and Institutional Review Board approval was obtained for each study site.

A total of 3,884 participants attended the 5th MESA examination in 2010 at one of the five field centers described above and are scheduled to return for the 6th MESA exam. The average age of these returning participants is 70.3 years; 44% are Caucasian, 36% are African American, and 55% are female. We are proposing to recruit our ancillary study population of 1,600 MESA participants from the 6th MESA exam.

Exclusion criteria specific to this ancillary study are the use of high dose vitamin D supplements (>1000 IU per day), use of any activated vitamin D analog (i.e. calcitriol), a clinical diagnosis of hyperparathyroidism, kidney dialysis or transplantation, a personal history of kidney stones within the previous 5 years, known clinical history of sarcoidosis, self-reported history of elevated serum calcium levels, or serum calcium greater than 11mg/dl at MESA Exam 1 (2000-2002). Each MESA field center will mail ancillary study materials to eligible participants in advance of Exam 6. These materials will explain the goals and procedures of this ancillary study.

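### Exclusion 9 cannot apply to MESA Family or Air New Recruit participants first recruited in 2004-2007, and no written rule acts on anyone's baseline serum calcium

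*Combined protocol and SAP*

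**What the plan says.** Section 4 lists as exclusion 9 "Serum calcium level >11 mg/dl at MESA Exam 1 (2000-2002". The protocol summary carries the same criterion, and section 12.1 A repeats it: "or serum calcium greater than 11mg/dl at MESA Exam 1 (2000-2002".

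Section 4 also dates the cohorts. Family participants are mainly "siblings and parents of MESA Classic participants who were recruited in 2004-2006 for genetics-based studies", and "MESA Air New Recruit participants were recruited in 2006-2007". Both groups may be approached for the trial, by telephone.

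The other criteria bearing on hypercalcaemia rest on history: known primary hyperparathyroidism (4), known sarcoidosis (7), and "Self-reported history of having elevated serum calcium levels" (8).

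Section 8.1 sets the baseline visit for the later cohorts: "All MESA Family and Air participants will use Exam 6-plus visits for basement measurements" (evidently meaning baseline). Besides consent, that visit comprises "a medical history focused on MESA-INVITe eligibility criteria, vital signs measurement, phlebotomy, urine collection, and study drug dispensing".

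Section 7.4 plans serum calcium at baseline and 16 weeks as a safety outcome. On stopping drug for an individual, section 6.5 says "Participants will be withdrawn from the study drug if they experience a significant adverse reaction related to the study drug". It adds intolerable reactions and withdrawn consent, and gives no calcium threshold. Section 12.1 B has calcium results mailed to participants after Exam 6A.

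**The concern.** A criterion that depends on a 2000-2002 blood value cannot exclude someone who first entered the cohort two or more years later. For those participants the sponsor's own limit of 11 mg/dl has no effect, and unrecognised hypercalcaemia would pass the history-based criteria. Blood is drawn and drug dispensed at one visit, so a high result would arrive after treatment had started, and the plan does not say what happens then. The scheduled two-week call is there to answer questions, support adherence and confirm the next appointment. Nothing links it to a laboratory result.

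Classic participants are only partly better placed. They have a value, but an old one, and no rule acts on their current calcium either.

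What is at stake is whether a safety limit that the sponsor chose can operate across the cohorts the protocol admits, when a measurement that could serve the purpose is already planned.

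**Working it through.** The plan gives no figure to reproduce. The check sets dates and rules side by side.

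**1. Can exclusion 9 operate?**
- Exam 1: July 2000 to August 2002 (section 12.1 A).
- Family: recruited 2004-2006. Air New Recruits: 2006-2007 (section 4).
- Both begin after Exam 1 closed, so a person first recruited then has no Exam 1 calcium and can never meet the criterion. The word *mainly* in the description of the Family cohort leaves room for a few who do have a value; the documents do not settle this.

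**2. How old is the Classic value at baseline?**
- Shortest gap: August 2002 to September 2016 (start of the Exam 6 window) = 14.1 years.
- Longest gap: July 2000 to January 2019 (planned close of enrolment) = 18.5 years.

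**3. Does any other rule act on a baseline calcium value?**
- Exclusions 4, 7 and 8: history only.
- Section 6.5: reactions and consent. Termination on the data safety monitoring board's finding acts on the trial, not on one participant.
- Section 8.1, Exam 6-plus: no result is awaited before dispensing.
- Section 9.2: conditions already present or found at screening are not recorded as adverse events unless they worsen.
- Section 12.1 B: results are mailed after follow-up.
- Result: none found.

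**4. Is the measurement in place?** Section 7.4 plans serum calcium at baseline, and the mailing in section 12.1 B presupposes it. However, the section 12.1 B list of assays on the shipped Exam 6 samples names urine calcium and not serum calcium. No run schedule or turnaround is given.

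**5. Size**
- Maximum daily intake from study drug and allowed supplements: 2,000 + 1,000 = 3,000 IU, against the stated upper intake of 4,000 IU.
- Still to enrol at the September 2018 plan, all cohorts: 682 - 523 = 159. The Family and Air share is not given.
- Planned active arm: 682 × 0.75 = 511.5, about 512. One early stop: 1/512 = 0.2%.
- Share of the 16-week dose avoided by stopping at day 14: 1 - 14/112 = 87.5%; at day 28: 1 - 28/112 = 75%. This is calendar arithmetic for a hypothetical participant on active drug. It measures dose, not risk.

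**The case against.** The best case against the point is that little is lost. Section 12.1 D says that this dose does not generally affect serum calcium, total intake stays under the upper limit, and the history-based exclusions cover every cohort. A value 14 to 18 years old looks more like use of data on file than a current screen, so the later cohorts lack little that Classic participants have. The plan speaks of up to three cohorts, and the Analytic Plan's list of steps to raise recruitment names neither Family nor Air, so the documents do not show that anyone from them enrolled. Acting on baseline calcium also costs more than one sentence: it needs prompt shipping, an alert procedure, and perhaps separate runs for baseline and follow-up calcium, which is itself an outcome.

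Most of this stands. It limits the size of the point and corrects its cost, but it does not supply the missing rule. The age of the Classic values argues for applying a rule to everyone rather than to no one. Reassurance about the dose in general says less about people above a limit that the sponsor itself set; section 9 notes that some studies saw small rises in serum and urine calcium.

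A reader might go further and infer that Family and Air participants enter unscreened for hypercalcaemia, that participants above the limit were treated, or that the trial's comparisons are biased. The documents support none of these. Exclusions 4, 7 and 8 still apply, no counts are given and they may be zero, and nothing here differs between the randomised arms.

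**Conclusion.** The gap is real and small. On the stated dates, the plan's only laboratory calcium limit cannot apply to Family or Air New Recruit participants first recruited in 2004-2007. For Classic participants it rests on a value about 14 to 18 years old. No written rule acts on anyone's baseline serum calcium.

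The safety gain from closing the gap cannot be quantified, because neither the number enrolled from the later cohorts nor the number above 11 mg/dl is given. The dose-avoided percentages should not be read as evidence of risk. No effect on the treatment comparison or the interaction tests is claimed.

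The conclusion assumes that participants in the later waves did not also attend Exam 1, and that no operating procedure outside these documents already reviews baseline calcium. The change is worth considering because the measurement is already planned.

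**What to change.** - **Section 4, summary and section 12.1 A:** state that exclusion 9 applies where an Exam 1 value exists.
- **Section 12.1 B:** add serum calcium to the list of assays.
- **Section 6.5:** add that baseline serum calcium is reviewed when available, at minimum for participants without an Exam 1 value and preferably for all. If it exceeds 11 mg/dl, study drug is stopped in either arm with the blind kept, and the participant is told. The sample precedes the first dose, so the result reveals nothing about allocation. Dispensing need not be delayed.
- **Analytic Plan, changes to the analytic plan:** define the treated participants in the active-arm-only analysis as those assigned to active drug, so that early stops stay in. Nothing else is needed here: section 8.2 already brings back participants who have stopped drug, and section 10 already analyses completers whatever their adherence.

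The cost is prompt shipping and assay, an alert call (the two-week call if the result is back by then, otherwise a separate one), and possibly baseline and follow-up calcium in separate runs, which would affect both arms equally. Rare early stops would slightly dilute the active-arm-only analysis, by about 0.2% of that arm each.

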5. RANDOMIZATION

Randomization will be performed centrally by the MESA data coordinating center (University of Washington, Seattle) in blocks of variable size (4-12), stratified by MESA study site.

Participants will be assigned to active vitamin D₃ or placebo in a 3:1 ratio, because short-term variability in response is expected to be substantially larger among participants who are assigned to active treatment.

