	Exclusion criteria 
1. Current use of >1,000 international units (IU) of cholecalciferol daily2. Current use of any activated vitamin D product (calcitriol, paricalcitol, hectorol)3. Known history of allergy or adverse reaction to vitamin D treatment4. Known clinical history of primary hyperparathyroidism5. Known clinical history of kidney stones within the previous 5 years6. Known clinical history of kidney dialysis or transplant.7. Known clinical history of sarcoidosis8. Self-reported history of having elevated serum calcium levels9. Serum calcium level >11 mg/dl at MESA Exam 1 (2000-2002)10. Current participation in another interventional study11. Inability to provide written informed consent
Study Duration	16 weeks
Treatment, Dosage, and Route of Administration	2,000 IU cholecalciferol or inactive placebo taken by mouth once daily
Efficacy Assessments	Change in serum 1,25-dihydroxyvitamin D concentration, serum parathyroid hormone concentration, and blood pressure from baseline to 16-week follow-up visit.

Safety Assessment	Change in urine and serum concentrations of calcium and phosphate from baseline to 16-week follow-up visit. Research staff will assess adverse effects during the study duration by participant self-report.
Modifying Characteristics	The following characteristics will be evaluated for their influence on the biological response to cholecalciferol treatment: genetic polymorphisms, serum concentrations of vitamin D metabolic markers, race, gender, and body mass index.
Statistical Methods	Linear models will be constructed for the follow-up value of each outcome variable. Models will include the initial value of the outcome variable, treatment assignment, and the interaction of treatment with the potential modifying variables.
Date of protocol	February 5, 2018

ABBREVIATIONS

MESA = Multi Ethnic Study of Atherosclerosis

1,25(OH)₂D = 1,25-dihydroxyvitamin D, the activated form of the hormone

25(OH)D = 25-hydroxyvitamin D, the accepted marker of vitamin D storage

Vitamin D₃ = cholecalciferol, the active treatment in the study

PTH = parathyroid hormone

IU = international units

UV = ultraviolet

AE = Adverse event

SAE = Serious adverse event

GFR = glomerular filtration rate

CHSCC = Collaborative Health Studies Coordinating Center

NORC = Nutrition and Obesity Research Center

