1. INTRODUCTION

Vitamin D is a vital metabolic hormone that may reduce the risks of cardiovascular diseases, cancer, fractures and other chronic health conditions. Traditionally understood as a calcium regulatory hormone, 1,25-dihydroxyvitamin D (1,25(OH)₂D, the potent hormonal form of vitamin D, binds to its target receptor to regulate the transcription of hundreds of genes relevant to health and disease. Vitamin D receptors are present in nearly all nucleated cells in the body, including those in cardiac muscle and the blood vessel wall. In experimental models, 1,25(OH)₂D promotes endothelial vasodilation, inhibits osteogenic differentiation of vascular smooth muscle cells, prevents cholesterol uptake in macrophages, reduces the progression of ventricular hypertrophy, and suppress the renin-angiotensin system. Cardioprotective actions of vitamin D are further supported by associations of low serum vitamin D concentrations with

hypertension, myocardial infarction, stroke, left ventricular hypertrophy, cancer, and mortality. Large clinical trials are currently testing whether vitamin D treatment will reduce the risks of cardiovascular disease, cancer, and other major health outcomes in the general population.

Published studies demonstrate substantial differences in the individual response to vitamin D treatment. Person-level differences in vitamin D treatment response may be caused by polymorphisms in vitamin D metabolism genes,

variation in race/ethnicity, and/or heterogeneity in functional vitamin D status. Vitamin D₃ (cholecalciferol) is generated in the skin upon exposure to UV light, consumed in the diet, or taken as supplements. Vitamin D₃ is then converted to 1,25(OH)₂D through a series of regulated steps that include transportation, metabolism, receptor binding, and catabolism. These processes are carried out by polymorphic proteins and enzymes that are subject to genetic variation and are closely regulated by internal vitamin D status. Differences in vitamin D metabolism by race and ethnicity have long been suspected due to differences in skin pigmentation. Cutaneous vitamin D₃ synthesis is lowest in African Americans compared to Caucasians; however, 1,25(OH)₂D concentrations are actually higher in African Americans, suggesting more efficient vitamin D utilization or slower vitamin D catabolism.

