10. ANALYTIC PLAN

We will describe MESA participants screened, enrolled, and completing this ancillary study according to CONSORT guidelines and compare characteristics of participants who do and do not pass through each of these stages. Primary analyses will include participants who complete baseline and 16-week follow-up regardless of adherence. Secondary analyses will include all consented participants using multiple imputation to address data missing from the 16-week follow-up visit.

We will construct linear models for the follow-up value of each outcome variable to determine whether common and rare polymorphisms in six candidate genes modify vitamin D₃ treatment effects: *CYP2R1*, *CYP24A1*, *CYP27B1*, *CYP3A4*, *SULT2A1*, and *VDR*. Independent variables in the model will include treatment group, number of minor alleles at a given locus, the interaction between treatment group and number of minor alleles, the baseline value of the outcome variable, and the following preselected precision variables: age, gender, BMI, season, and the estimated glomerular filtration rate (GFR). Given sample size limitations we will conduct primary genetic analyses among only the white and Black subgroups with potential associations carried to the Chinese and Hispanic groups. Power to detect genetic associations of common variants are shown in Table 1. Secondary genetic analyses are planned to explore all measured and imputed genetic variants with >5% minor allele frequency derived from the Affymetrix 6.0 chip and 1000 Genomes imputation using the regression framework described above.

Table 1. Power for analyses of common variants.

Minor allele frequency	All	White	Black
0.1	0.013	0.001	0.001
0.2	0.141	0.013	0.006
0.3	0.357	0.045	0.021
0.4	0.521	0.083	0.041

We will test whether race/ethnicity, gender, body mass, index, estimated GFR, and serum concentrations of 25(OH)D, bioavailable 25(OH)D, and 24,25(OH)₂D₃ modify the response to vitamin D₃ treatment using analogous regression models to those described above.

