The overall design of the study has not changed. INVITE remains a randomized two-arm, double-blind clinical trial with a 3:1 ratio of assignment to active vitamin D treatment versus placebo. We discussed the possibility of removing the placebo group to create a treatment only study; however, implementing such a change after recruitment of greater than 75% of participants would be difficult to explain to the DSMB, the MESA study sites, and the participants themselves. Moreover, we believe that such a change in design would diminish the impact of manuscripts resulting from this study.

Unlike typical event driven trials, INVITE seeks to identify characteristics that modify the response to treatment. To increase study power to detect such associations, we will start by evaluating only participants who are treated with active vitamin D to assess main effects of genetic polymorphisms and clinical characteristics on the changes in study outcomes. In parallel we will present analytic results from our original approach, in which we analyze all participants and test the interaction of relevant exposures with treatment assignment.

Changes to sample size and study power

Study power for the treatment only analytic approach is considerably greater than that of the original interaction-based analyses. Differences in the effect of vitamin D treatment on study outcomes of change in parathyroid hormone, 1,25-dihydroxyvitamin D, and urine calcium to creatinine ratios according to a modifying genetic polymorphism are presented below. Under the anticipated sample size of 682, the INVITE study will maintain power to detect clinically relevant associations. The INVITE DSMB, which includes a faculty biostatistician, met on September 13, 2018, at which time it reviewed and approved these changes to the analytic plan and power.

Figure2. Minimal detectable associations for genetic polymorphisms under a treatment-only analysis.

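### At 3:1 allocation the treatment-by-modifier models specify no arm-specific variance, so an ordinary pooled fit gives a wrong interaction standard error whenever the residual SDs differ by arm

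*Combined protocol and SAP*

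**What the plan says.** Section 5 (Randomization) gives one reason for allocating 3:1: "short-term variability in response is expected to be substantially larger among participants who are assigned to active treatment". The Introduction points the same way: "Published studies demonstrate substantial differences in the individual response to vitamin D treatment".

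The Protocol Summary, under Statistical Methods, lists the model terms: "Models will include the initial value of the outcome variable, treatment assignment, and the interaction of treatment with the potential modifying variables". Section 10 (Analytic Plan) repeats this for the genetic models: "We will construct linear models for the follow-up value of each outcome variable". Their terms include "the interaction between treatment group and number of minor alleles, the baseline value of the outcome variable", together with age, gender, BMI, season and eGFR as main effects. Gender, body mass index and eGFR also appear in section 10 as candidate modifiers in their own right. The analyses are then cut by race: "Given sample size limitations we will conduct primary genetic analyses among only the white and Black subgroups".

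The 2018 Analytic Plan, under its changes to the analytic plan, puts an active-arm-only analysis first and retains the interaction models: "In parallel we will present analytic results from our original approach". It adds: "Study power for the treatment only analytic approach is considerably greater than that of the original interaction-based analyses". No section names a variance structure, a weighting scheme or a standard-error estimator, and none is ruled out.

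**The concern.** The design expects unequal variability between arms, but the stated analysis makes no provision for it. In an ordinary regression one residual variance serves both arms, and at 3:1 it is mostly the active arm's. The interaction estimate depends heavily on the small placebo arm, so applying the active arm's variance there distorts its standard error. At 1:1 the distortion would cancel; it arises from the unequal allocation.

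The interaction analysis is the only one that uses the randomised placebo comparison. It alone can separate modification of the treatment effect from a characteristic's association with change regardless of treatment. By the plan's own account it is already the weaker of the two analyses, so an avoidable loss of power, or an uncontrolled error rate, matters most there.

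**Working it through.** **Inputs.** Allocation is 3:1 (section 5). The anticipated sample is 682 (Analytic Plan), about 512 active and 170 placebo. No SD, variance ratio, significance level or effect size is stated. For the same reason Table 1 of section 10 (power 0.013 to 0.521 overall, 0.001 to 0.083 in the White and Black columns) cannot be reproduced. Every r below is an assumption.

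**Standard-error factor.** Set the placebo residual variance to 1 and the active one to r². Randomisation makes the modifier's variance v the same in both arms in expectation.

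- True interaction variance: (r²/0.75 + 1/0.25)/(Nv) = (4/3)(r²+3)/(Nv).
- Pooled-fit variance: (0.75r²+0.25)(1/0.75+1/0.25)/(Nv) = (4/3)(3r²+1)/(Nv).
- Model SE / true SE: R = sqrt((3r²+1)/(r²+3)), whatever N is. At 1:1 the corresponding ratio is exactly 1.

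The size of a nominal 5% test is 2(1−Φ(1.96R)). Power that would be 80% with the correct SE becomes Φ(1.96+0.8416−1.96R). For r = 1.5, R = sqrt(7.75/5.25) = 1.21.

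| Residual SD ratio r | R | Size at 5% | Power (80% with correct SE) |
|---|---|---|---|
| 1.1 | 1.05 | 4.0% | 77% |
| 1.25 | 1.12 | 2.9% | 73% |
| 1.5 | 1.21 | 1.7% | 66% |
| 2 | 1.36 | 0.8% | 55% |

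The proportional loss grows at stricter thresholds: at 0.1% the same four ratios give 75%, 68%, 55% and 36%. In the other direction, r = 0.9 and 0.8 give sizes of 6.3% and 7.9%.

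**From response variability to residual variability.** Section 5 speaks of response; the formula needs the residual. Let response heterogeneity have variance h² = r0²−1, where r0 is the ratio if none of it runs through the model covariates (independence assumed). Let a share s run through covariates fitted only as main effects. A common slope fitted at 3:1 lies three-quarters of the way to the active-arm slope, so the misfit is (1/4)² = 1/16 of that part in the active arm and (3/4)² = 9/16 in placebo:

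- active residual variance = 1 + (1−s)h² + s·h²/16
- placebo residual variance = 1 + 9s·h²/16

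For r0 = 1.5 and s = 0.5, h² = 1.25. The variances are 1.664 and 1.352, so r = 1.11.

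| r0 | s = 0.5: r, power | s = 1: size at 5% |
|---|---|---|
| 1.25 | 1.06, 78% | 6.5% |
| 1.5 | 1.11, 77% | 8.0% |
| 2 | 1.19, 75% | 10.7% |

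With s = 1 the residual ratio drops below 1 (for r0 = 1.5: variances 1.078 and 1.703, r = 0.80), and the pooled test is liberal. The shares are assumptions; the documents give none.

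**Simulation.** At 512/170, minor allele frequency 0.3 and r = 1, 1.1, 1.25, 1.5, 2, pooled power was 78.9%, 76.0%, 71.7%, 65.0% and 54.0%. With separate variances it was 78.7% to 78.9% throughout. In a Black-sized subgroup (36% of 682, the share in section 12.1, assumed to carry over: 184/61), frequency 0.1 and r = 1, 1.25, 1.5, 2, pooled size at 5% was 4.99%, 2.94%, 1.80% and 0.87%. REML with variance by arm and Satterthwaite degrees of freedom gave 4.98% to 5.05%. At r = 0.8 the figures were 7.9% pooled and 4.95% separate. HC3 gave sizes of 4.5% to 5.7% at totals of 682 and 1,600. The default sandwich (HC1) gave 6.0% to 6.6% at r = 1.25 to 2. The simulations of the fix imposed r directly, with normal errors; none generated the heterogeneity through covariates.

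**The case against.** The strongest objection is that section 5's expectation does not fix the sign of the error. A reader might infer that the pooled standard error must be too large and the tests conservative. That does not follow. Baseline value, gender, BMI and eGFR enter the genetic models as main effects, and some of them are themselves candidate modifiers. Heterogeneity that runs through them falls mostly into the placebo residual, which shrinks r and can take it below 1. This stands. Above-1 ratios remain the likelier case only if most heterogeneity is unexplained by these covariates.

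A reader might also take a fall from 80% to 55% as this trial's loss. Table 1 does not support that. It was drawn up when 1,600 was the target, and its subgroup power is at most 0.083, so no subgroup test in it can lose more than 8.3 points. The 80% starting point is only a reference.

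Third, the plan nowhere says pooled variance. That is right: the point is conditional on an ordinary fit, which is the usual reading of linear models when nothing else is named.

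Last, the active-only analysis now leads and is unaffected. This lowers the practical weight but does not remove the point, because the interaction results will still be reported and are the only placebo-controlled test of modification.

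**Conclusion.** The concern holds in conditional form. An ordinary pooled fit at 3:1 gives a wrong interaction standard error whenever residual SDs differ by arm, and the protocol gives its own reason to expect that they may. For assumed residual ratios of 1.1 to 2 the standard error is 5% to 36% too large, and illustrative 80% power falls to between 77% and 55%. If half the heterogeneity runs through model covariates, the loss is only 2 to 5 points for ratios that would otherwise be 1.25 to 2. If all of it does, the error reverses and a 5% test has size 6.5% to 10.7%. Absolute losses in the planned genetic tests may be smaller than the illustration, since stated power is well below 80%. Pooling the variance does not bias the point estimates. The formula is firm; the size and the direction rest on ratios and shares that the documents do not give. The change is worth making because it protects in both directions at little cost.

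**What to change.** State in the analytic plan that the interaction models will be fitted with a separate residual variance in each arm, by REML with Satterthwaite or Kenward-Roger degrees of freedom, or with a small-sample robust standard error such as HC3. Do not use HC1 in the small race subgroups. HC3 was checked only at totals of 682 and 1,600, so check its calibration in the subgroups before relying on it there. Report the residual SD by arm for each outcome, so that readers can see which way a pooled fit would have erred.

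Check calibration by simulation or permutation before using very strict genetic thresholds or analysing skewed outcomes. At nominal 0.01% the simulated REML size ranged from 0.007% to 0.014% (Monte Carlo SE 0.0016%), which does not settle behaviour at stricter levels.

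The cost is a few sentences, standard software and no new data, with somewhat more computing if REML is run for every variant in the secondary genetic analyses. If the SDs are in fact equal, separate variances cost 0.2 power points at 512/170 (78.9% to 78.7%) and 0.4 at 184/61 (75.9% to 75.5%). Effective degrees of freedom also fall, because the placebo arm is small.
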